#### **5.4.2 *Masking Procedures***

In this RCT, it is not feasible to blind patients, surgeons, or dental assistants to treatment after the intervention assignments have occurred, so they will not be blinded. It is, however, feasible to mask the sequence of treatment assignments until the moment each assignment is made, and this will be done, as described in Section 5.4.1, above.

The DCC will also be un-blinded to treatment arm assignment. However, study staff and investigators will not have access to any interim outcome data. Unmasking procedures during the surgery will not be necessary as the patient, surgeon, and dental assistants will be un-blinded to the treatment group for each patient. The patient's record in the OMS office will include documentation of study participation and their group assignment (i.e., UC versus EC).

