#### Enrollment/Baseline Visit (Visit 1, Day 0)

- Verify, obtain and document consent from potential patient via electronic data capture consent form based on IRB requirements.
- Verify and document Health Insurance Portability and Accountability Act (HIPAA) authorization for use of the patient's Personal Health Information (PHI) in Research, based on IRB requirements.
- Patient completes patient contact information, patient demographics information, and *Baseline Patient Questionnaire*.
- Record results of TMD examination from OMS on *Doctor Surgery Questionnaire*.

- After a patient eligibility is confirmed and they have provided consent, the patient's random assignment to EC or UC is then automatically available to the OMS and their dental assistant on the tablet. The patient is then informed of their group assignment.
- OMS completes usual care extraction of 3rd molars with moderate/deep sedation or general anesthesia and bite block. If patient is randomized into the UC group, the procedure will be completed with a bite block and a DA holding the jaw. If patient is randomized into the EC group, the procedure will be completed with a bite block and the RJ2 device.
- OMS completes *Doctor Surgery Questionnaire*.

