## 12.4 Final Analysis Plan

All analyses will be by intention-to-treat, with participants included in the group (UC or EC) to which they were randomly assigned.

**Primary analysis.** The primary outcome is incidence of TMD pain within a 6-month follow-up period (a binary dependent variable). The incidence of TMD pain post-surgically will be compared between UC and EC groups. This primary TMD outcome is deemed to have occurred if the patient's self report in the *Patient 1-, 3- and 6-month Follow-up Questionnaires* endorses either or both of the following questions: Pain in jaw with wide opening, or pain in temples, jaw joints or jaw muscles. The primary analysis will include all available follow-up measures (1, 3, and 6 months) for each participant to

estimate incident TMD pain. The UC and EC groups will be compared using an analysis that has the form of logistic regression, but which accounts for correlation of visits within participants using generalized estimating equations (GEE) with each participant being a cluster. The analysis will include group (UC vs. EC), which tests whether the two groups differ in overall frequency of TMD pain; time (1, 3, and 6 months, as a categorical factor); and their interaction (i.e., the time-by-group interaction), which tests for different patterns of change over time in frequency of TMD pain.

In the event of noteworthy amounts of missing data (e.g., patients lost to follow-up or questionnaires not completed), we will check the primary analysis by using standard multiple imputation methods, as implemented in the most recent version of the SAS software (SAS Institute Inc., Cary NC, v. 9.4 or higher), to multiply impute missing data and perform tests. Specifically, we will use SAS's FCS method to create 20 "complete" datasets and otherwise use the defaults in SAS's procedures.

**Secondary analysis.** The primary analysis will not include adjusters, as the randomization should balance the groups. As a check on this, an adjusted version of the primary analysis will include adjusters differing substantially between the two randomized groups, selected from the list of potential adjusters given below (see "Potential Adjusters", below).

Other secondary analyses are as follows:

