1. The incidence of TMD pain, as measured with the validated *TMD Pain Screener Questionnaire* (*binary dependent variable*), will be compared between the UC and EC groups within a 6-month follow-up period based on patients' self report in the *Patient 1-, 3- and 6-month Follow-up Questionnaire*. These analyses will have the same form as the primary analysis.
2. TMD pain intensity, as measured with the validated Characteristic Pain Intensity (CPI) within a 6-month follow-up period (treated as a continuous measure), will be compared between the UC and EC groups based on patients' self report in the *Patient 1-, 3- and 6-month Follow-up Questionnaire*. Unadjusted and adjusted analyses (using adjusters selected as described above) will be performed using GEE as in the primary analysis.
3. Baseline characteristics, specifically all of the potential adjusters listed below (see "Potential Adjusters", below), will be compared between the UC and EC groups. Analyses will use t-tests, possibly after transforming the measure because it has a skewed distribution, Chi-squared test and Fisher's Exact Test.

4. The UC and EC groups will be compared for TMJ noise, pain characteristics (e.g., location in temple or jaw, and occurrence with wide opening of mouth) and change in jaw pain since it started, within a 6-month follow-up period based on patients' self report in the *Patient 1-, 3- and 6-month Follow-up Questionnaire*. These analyses will have the same form as the primary analysis.
5. A descriptive summary of the experiences of surgeons and dental assistants with the new device at mid-way through recruitment of patients and at the end of recruitment based on their self report in the *Doctor Questionnaire Regarding Use of the Device* and *Dental Assistant Questionnaire Regarding Use of the Device*, respectively,

All analyses will use SAS version 9.4 or later (SAS Institute Inc., Cary, NC). All tests will use a significance threshold of 0.05 (2-tailed).

Potential adjusters: The following characteristics will be compared between the UC and EC groups as potential adjusters:

- Patient demographics
- Baseline patient-reported symptoms (e.g., TMJ noise, pain or discomfort around wisdom teeth, frequency of oral habits as measured with the Oral Behaviors Checklist (OBC), and health status; see *Patient Baseline Questionnaire*).

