- Baseline clinical findings by the surgeon (e.g., TMJ noise, eruption status, pericoronitis, soft-tissue infection, reason for extraction, difficulty of extraction, length and duration of the surgery, and pain or discomfort around third molars); see *Doctor Surgery Questionnaire*.
- Procedural characteristics, identified by the surgeon (e.g., type of extraction, amount of bone removal, use of grafting); see *Doctor Surgery Questionnaire*.

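### The adjusted secondary analyses can adjust for surgery duration and other intra-operative variables that the plan calls baseline, chosen because they differ between arms

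*Combined protocol and SAP*

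**What the plan says.** Section 12.4 keeps the primary analysis unadjusted: "The primary analysis will not include adjusters, as the randomization should balance the groups". As a check on that balance, "an adjusted version of the primary analysis will include adjusters differing substantially between the two randomized groups". The same selection feeds the CPI analysis in item 2: "Unadjusted and adjusted analyses (using adjusters selected as described above) will be performed using GEE as in the primary analysis".

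Item 3 labels the whole list of candidates: "Baseline characteristics, specifically all of the potential adjusters listed below". Under the surgeon's baseline clinical findings, that list includes "difficulty of extraction, length and duration of the surgery, and pain or discomfort around third molars". A separate bullet adds "Procedural characteristics, identified by the surgeon (e.g., type of extraction, amount of bone removal, use of grafting".

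On timing, Section 7.2 (Visit 1) says that before the extractions the patient's "random assignment to EC or UC is then automatically available to the OMS and their dental assistant on the tablet". Sections 4 and 8.1 have the surgeon complete the Doctor Surgery Questionnaire, the stated source of these items, once surgery is over. Section 5.4.2 says that "it is not feasible to blind patients, surgeons, or dental assistants to treatment after the intervention assignments have occurred". Nothing in the plan limits adjusters to variables fixed before randomization.

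**The concern.** A difference between arms in a true baseline variable is chance. A difference in a variable that arises after randomization may be an effect of the device. A rule that picks variables because the arms differ cannot tell the two apart, and among post-randomization variables it tends to pick those the device has altered.

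The protocol's rationale (Section 2.2) supplies a possible path through duration. With hand support, the operation pauses if more intravenous medication is needed. A long extraction is said to be able to injure the jaw. The device would free the assistant's hands. If the device shortens surgery, adjusting for duration removes part of a real benefit. If it lengthens surgery, adjusting overstates the net benefit. Difficulty ratings that depend on the known arm, or unmeasured causes of both long surgery and pain, could bias the estimate in either direction.

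Because the adjusted model is offered as a check on randomization, a shift in it is likely to be taken for chance imbalance.

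**Working it through.** **Order of events.** Eligibility and consent, then the assignment shown on the tablet (7.2), then surgery, then the surgeon's form (4, 8.1).

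| Candidate adjuster | Position relative to assignment |
|---|---|
| Duration of surgery | After, necessarily |
| Difficulty of extraction | On the form completed after surgery by an unblinded surgeon; the moment of rating is not stated |
| Extraction type, bone removal, grafting | Recorded after assignment; no device effect is indicated |
| Eruption status, pericoronitis | Status exists before assignment, but recorded on the same post-surgery form |
| Demographics, patient-reported baseline items | Before |

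**The plan's own figure.** For 28% vs 14%, two-sided 5%, 80% power:

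n = [1.96·√(2·0.21·0.79) + 0.8416·√(0.28·0.72 + 0.14·0.86)]² / 0.14² = (1.129 + 0.478)² / 0.0196 = 131.7

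This matches the 132 per group in Section 12.2 and Table 1. The odds ratio for this pair is (0.14/0.86)/(0.28/0.72) = 0.42. It serves below as the true total effect.

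**Chance that duration is selected.** Assumption: differing substantially means t-test P<0.05. For a device effect of δ SD, the statistic is noncentral t with 262 df and noncentrality δ·√(132/2).

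| δ (SD) | Noncentrality | Chance selected |
|---|---|---|
| 0 | 0 | 5% |
| 0.1 | 0.81 | 13% |
| 0.2 | 1.62 | 37% |
| 0.3 | 2.44 | 68% |
| 0.5 | 4.06 | 98% |

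**Effect on the adjusted estimate.** Assumed model: a single binary outcome, as in Section 12.2; duration D normal with SD 1 and mean shifted in the EC arm; logit P(pain) = α + β·EC + log(1.5)·D. The terms α and β are solved by numerical integration so that the marginal risks stay at 28% (UC) and 14% (EC). The adjusted odds ratio is exp(β). Power is by simulation with 132 per arm and Wald tests.

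| Surgery with the device | Adjusted OR | Power if duration is in the model | Power if duration is adjusted for only when selected |
|---|---|---|---|
| No change | 0.41 | – | – |
| 0.1 SD shorter | 0.43 | 78% | 79% |
| 0.2 SD shorter | 0.44 | 73% | 75% |
| 0.3 SD shorter | 0.46 | 68–69% | 70% |
| 0.5 SD shorter | 0.50 | 57% | 57% |
| 0.2 SD longer | 0.38 | 87–88% | 84% |
| 0.5 SD longer | 0.33 | 92–93% | 92% |

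Unadjusted power is about 80% in every row. The 0.41 with no change in duration reflects non-collapsibility of the odds ratio alone. For duration odds ratios of 1.3 to 1.8, the entry at 0.5 SD shorter runs from 0.47 to 0.54. Among trials that select duration, the share of significant unadjusted results that become non-significant is about 14–16% at 0.2 SD and 28–29% at 0.5 SD.

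**Bias without a true effect.** In a second illustration the device shortens surgery by 0.5 (error SD 1) but has no effect on pain, and duration itself does not affect pain. An unmeasured factor raises both duration and the log-odds of pain (coefficient 0.7 on each). The unadjusted odds ratio is 0.99 and the adjusted one 1.16. Duration is selected in about 93% of trials.

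**The case against.** The strongest reply is that only supportive analyses are touched, through an effect nobody has measured. The primary result stays unadjusted, and no device effect on duration, duration–pain association or variance appears in the documents. The time item named in Section 8.1 is an estimate of extraction time, which may not capture pauses. The illustration also uses one binary outcome, not the planned GEE over three visits. All of this stands. It limits the weight of the point and makes the figures illustrative.

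Second, difficulty might be judged before the operation. Section 8.1 does not name it among the form's items, and Section 7.2 shows that the same form also takes the TMD examination, listed before assignment. This is fair: for difficulty the case rests on when the form is completed and on the surgeon knowing the arm. For duration there is no such doubt.

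Third, the selection threshold may not be open. Item 3 of Section 12.4 compares the candidates by formal tests, and the section sets 0.05 for all tests. That is the natural reading and the one used above, but the plan does not tie it to the selection rule. A firm threshold would not cure the problem, because the criterion would still be a difference between arms.

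Fourth, power computed as if duration were always in the model overstates the loss when selection is uncertain. This is correct at small effects (75% instead of 73% at 0.2 SD), and both columns are shown for that reason.

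**Conclusion.** The concern holds. As written, the plan calls intra-operative variables baseline, allows them as adjusters and selects them by between-arm difference. The adjusted primary-outcome model and the adjusted CPI analysis can therefore condition on something the device has changed. The unadjusted primary estimate and test stand, as do the sample size and the secondary analyses that share the primary's unadjusted form.

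The size depends on an unknown device effect on duration. Under the stated assumptions it is negligible at 0.1 SD, modest at 0.2 SD (odds ratio 0.42 to 0.44) and material at 0.5 SD (0.42 to 0.50, with power falling from 80% to about 57%). The bias reverses if surgery takes longer. The finding itself rests on the order of events and the selection rule, not on these figures. It is certain for duration, probable for difficulty, and for extraction type, bone removal and grafting rests only on their being recorded after randomization.

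**What to change.** - Remove duration, difficulty, extraction type, bone removal and grafting from the potential adjusters. Keep the planned comparison by arm, but present them as procedural outcomes and not as baseline characteristics.
- Replace selection by observed difference with one set named in advance on prognostic grounds, used for both adjusted analyses: surgeon (the stratification factor), demographics, patient-reported baseline TMJ noise, third-molar pain, Oral Behaviors Checklist score, general health, and pre-operative findings such as eruption status and pericoronitis.
- Because those last findings sit on the post-surgery form, either have them entered before the assignment is shown or state the limitation.
- Do not add baseline jaw or temple pain to the set. The exclusion of patients with TMD pain in the past 3 months (Section 5.2) leaves it nearly constant.

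The cost is a wording change in Section 12.4, since all the variables are already collected. Entering the pre-operative items earlier is optional and would be a small change to the order of the electronic form, with matching text in Sections 4, 7.2 and 8.1.

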## **13 SOURCE DOCUMENTS AND ACCESS TO SOURCE DATA/DOCUMENTS**

Each participating office will maintain appropriate medical and research records for this study, in compliance with ICH E6, Section 4.9 and regulatory and institutional requirements for the protection of confidentiality of subjects. Study staff will permit authorized representatives of NIDCR and regulatory agencies to examine (and when required by applicable law, to copy) research records for the purposes of quality assurance reviews, audits, and evaluation of the study safety, progress and data validity.

The following will be considered source documents maintained by the DCC via electronic data management system or paper:

- Surgeon log of eligible and ineligible patients who did not enter study
- OMS consent (if applicable)
- Dental Assistant consent
- Patient consent
- Patient HIPAA
- Patient contact information
- Patient demographics information
- Patient Baseline Questionnaire
- Patient One-Month Follow-up Questionnaire
- Patient Three-Month Follow-up Questionnaire
- Patient Six-Month Follow-up Questionnaire
- Screening Questionnaire
- Doctor Surgery Questionnaire
- Doctor Questionnaire Regarding Use of Device
- Dental Assistant Questionnaire Regarding Use of Device

## **14 QUALITY CONTROL AND QUALITY ASSURANCE**

Data collection for this trial will occur via an electronic data capture (EDC) system that employs on-screen data validation and alerts. In addition, key data elements may need to be double entered, or reviewed and affirmed, to confirm correct data entry.

Prior to EDC system development, the system specifications will be carefully evaluated by the study team, DCC, and other stakeholders as necessary (e.g., NIDCR program official). Prior to study launch, the EDC system will undergo user acceptance testing, which will be documented in the Test Summary Report. Further, a data management plan developed by the DCC details quality management procedures including the development of data quality checks in the database system and processes related to quality review and management of data entered.

The architecture of the EDC system and rigorous testing of it prior to study launch provide built-in procedures for maintaining data quality. Additionally, the DCC will produce reports, periodic (at least monthly) and real-time, to monitor data quality. For example, this includes monitoring to ensure present and valid entries in given data fields. Report design will consider available resources in the NIDCR Toolkit for Clinical Researchers (e.g., the NIDCR Quality Management Subject Participant Data Review Tool).

## **15 ETHICS/PROTECTION OF HUMAN SUBJECTS**

### **15.1 Ethical Standard**

The PI will ensure that this study is conducted in full conformity with the principles set forth in The Belmont Report: Ethical Principles and Guidelines for the Protection of Human Subjects of Research, as drafted by the US National Commission for the Protection of Human Subjects of Biomedical and Behavioral Research (April 18, 1979) and codified in 45 CFR Part 46 and/or the ICH E6.

### **15.2 Institutional Review Board**

The protocol, informed consent form(s), recruitment materials, and all subject materials will be submitted to the IRB at the University of Minnesota and HealthPartners for review and approval. Approval of both the protocol and the consent form must be obtained before any patient is enrolled. Any amendment to the protocol will require review and approval by the IRB before the changes are implemented in the study.

### **15.3 Informed Consent Process**

Informed consent is a process that is initiated prior to the individual agreeing to participate in the study and continues throughout study participation. Extensive discussion of risks and possible benefits of study participation will be provided to patients and their families, if applicable. A consent form describing in detail the study procedures and risks will be given to the patient. Consent forms will be IRB-approved, and the patient is required to read and review the document or have the document read to him or her. The OMS and staff, with appropriate training, will explain the research study to the patient and answer any questions that may arise. The patient will sign the informed consent document prior to any study-related assessments or procedures. Patients will be given the opportunity to discuss the study with their surrogates or think about it prior to agreeing to participate. They may withdraw consent at any time throughout the course of the study. A copy of the informed consent document will be given to patients for their records. The rights and welfare of the patients will be protected by emphasizing to them that the quality of their clinical care will not be adversely affected if they decline to participate in this study. When consenting the OMS (when applicable) and dental assistants, they will be informed that their participation is voluntary and employment is not contingent on participation.

The consent process will be documented in the clinical or research record.

#### **15.4 Exclusion of Women, Minorities, and Children (Special Populations)**

Racial and ethnic minorities will be included in the study at least proportional to the composition in the dentist's patient population. Individuals of any sex or racial/ethnic group may participate. Patients 18 – 30 years of age will be included in this study.

#### **15.5 Subject Confidentiality**

Patient confidentiality is strictly held in trust by the investigators, study staff, and the sponsor(s) and their agents. This confidentiality is extended to any study information relating to patients.

The study protocol, documentation, data, and all other information generated will be held in strict confidence. No information concerning the study or the data will be released to any unauthorized third party without prior written approval of the sponsor.

The study monitor or other authorized representatives of the sponsor may inspect all study documents and records required to be maintained by the investigator, including but not limited to, dental records (office, clinic, or hospital) for the study patients. The clinical study site will permit access to such records.

The security features of the data capture system will enforce strict limits on data access for various members on the team. The system will be configured to give study personnel “minimum necessary” access to data given the role of the person in the project.

**Certificate of Confidentiality:** To further protect the privacy of study participants, the NIH will issue a Certificate of Confidentiality. This certificate protects identifiable research information from forced disclosure. It allows the investigator and others who have access to research records to refuse to disclose identifying information on research participation in any civil, civil, criminal, administrative, legislative, or other proceeding, whether at the federal, state, or local level. By protecting researchers and institutions from being compelled to disclose information that would identify research subjects, Certificates of Confidentiality help achieve the research objectives and promote participation in studies by helping assure confidentiality and privacy to subjects.

